10.2 Reporting Procedures

➤ **Reporting of Adverse Events to FDA**

- **Written IND Safety Reports (if applicable)**
- **Telephoned IND Safety Reports – Fatal or life-threatening suspected adverse reactions**

➤ **Reporting Adverse Events to the Partner Human Research Committee**

The Partners Human Research Committee (PHRC) policy for "REPORTING ADVERSE EVENTS AND UNANTICIPATED PROBLEMS" will be followed.

➤ **Reporting Adverse Events to External Parties**

Adverse events will be reported to the USArmy's Human Research Protections Office (HRPO) and the US Food and Drug Administration per their guidelines. Certain adverse events, specifically infections with positive donor rim cultures, that are related to the cornea donor tissue will be reported to CorneaGen within 48 hours of discovery.

10.3 Termination, of Subjects due to Adverse Events

Termination from the study will happen if any of the following occurs:

- Subject's wish to withdraw for any reason.

- Investigator or Research Monitor determination that it is not in the best interest of the subject to continue participation
- KPro removal

In the event an adverse event in the study eye is severe enough to require the donor study tissue to be removed and replaced with fresh cadaveric human cornea donor tissue with or without a keratoprosthesis, the patient will be terminated from further participation in the study. However, prior to termination the patient will be followed for 30 days after replacement surgery to collect any additional event data.

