6.8 Rescue Medication or Therapy

Subjects who do not retain the cross-linked KPro will be withdrawn from the study and the cornea will be replaced with a cadaver cornea or standard KPro at the physician's discretion.

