8.6 Follow-up Procedures

Additionally, to determine the safety and efficacy of using riboflavin-ultraviolet light induced collagen cross-linked cornea tissue in promoting retention, follow-up visits will be scheduled at Day 1 and 7 (± 3 days), week 4 (± 3 days), week 16 (± 2 weeks), week 24 (± 3 weeks), week 36 (± 3 weeks), and week 52 (± 4 weeks). Following week 52 visit, standard of care visits will occur every six months. The study will continue to collect data from these standard of care visits (post week 52 visit) in order to monitor subject safety for an additional 3 years or until study closure. Any procedures/exams performed during these visits will be standard of care and the MD will decide which procedures/exams are needed. Study staff will collect data for any procedures/exams that may be conducted as they pertain to the study (changes in medical history and medication prescription; BCVA, slit-lamp exam, IOP, funduscopy/B-Scan, OCT images, slit lamp photography and review of potential adverse events).

A description of imaging procedures follow in this section and a table of follow-up procedures organized by time-point can be found in section 7.7 below.

Cornea Thickness as measured by AS-OCT

Because corneal thinning will be used as a secondary endpoint and is an indication of corneal melts, cross- sections of the cornea will be obtained using anterior segment AS-OCT. This non-contact high-resolution imaging modality provides cross-sectional images of the cornea and anterior segment with a resolution of approximately 5-18 μ m. To evaluate the cornea, cross-sectional OCT images will be obtained at 0, 45, 90, 135, 180, 225, 270, 315 and 360 degrees.

Slit Lamp Photography

Because it is possible that slit lamp findings may be predictive of keratoprosthesis loss or corneal thinning, digital corneal photography will be done using a slit-lamp with a digital camera attachment and a flash-through-the-slit illumination system. By fine focusing on the surface of the cornea prior to corneal transplant surgery at the screening visit, and at Week(s) 1, 4, 16, 24, and 52, the photographer will capture the entire cornea using diffuse illumination and 10x magnification. If lids are drooping, the photographer will attempt to gently remove them from area of focus with a cotton swab.

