8.8 Early Termination

Subjects have a right to withdraw from the study at any time. Additionally, the subject may be withdrawn from the study for any reasons: if it is in the best interest of the subject, intercurrent illness, adverse events, or worsening condition. The site investigators or Medical Monitor may request the withdrawal of a subject because of protocol violations, administrative reasons, or any other valid and ethical reasons.

Reasons for subject termination may include, but are not limited to, the following:

- Investigator determination that it is not in the best interest of the subject to continue participation
- Serious adverse events

- Any other safety concerns

In the event of an adverse event in the study eye that is considered by the investigator or Research Monitor to be severe in intensity, the donor tissue will be removed and replaced with fresh cadaveric human cornea donor tissue with or without a keratoprosthesis, discontinuing the patient from further participation in the study.

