8.9 Schedule of Activities (Study Table)

	Screen	Day 0	Day 1	Wk. 1	Wk. 4	Wk. 16	Wk. 24	Wk. 36	Wk. 52
Visit Window	-60 days		+3 days	± 3 days	±3 days	± 2 weeks	± 3 weeks	± 3 weeks	± 4 weeks
Informed consent (study and surgical)	X								
Demographic data	X								
Medical/surgical history/chart review	X								
Review of Systems	X								
BCVA ***	X								
Slit-lamp exam***	X								
IOP ***	X								
Funduscopy/ Ultrasound B-scan (if necessary)***	X								
Contact Lens Review									
Pregnancy Test*	X								
Cornea thickness as measured by AS-OCT									
Slit Lamp Photography***	X								
Review Adverse Events									
Concomitant Medication Check	X								

Subjects will be instructed to strictly follow the study visit schedule.

* An additional urine pregnancy test needs to be performed just prior to surgery if there is greater than 30 days between screening visit and surgery.

**All subjects will be followed for at least 2 years. Following week 52 visit, standard of care visits will occur every 6 months for an additional 3 years or until study closure.

*** Historical results for best corrected VA, intraocular pressure, slit lamp examine, slit lamp photography and funduscopy can be used if completed within 60 days prior to screening visit

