10. ADVERSE EVENT RECORDING AND REPORTING

10.1 Recording Requirements

Participants are informed of the anticipated risks of the trial during the consent process and continually asked to report any unusual ocular or systemic problems that occur during their participation in this trial to the site investigators or study staff. In addition, participants are seen regularly in site clinics as part of their standard post-surgical treatment. During each clinical examination participants will be queried about occurrence of adverse events. Slit lamp examination and ocular assessments will determine change in corneal thickness and or presence of corneal ulcers. Lastly, site investigators and study staff will be asked to report unanticipated problems or adverse events within 48 business days of discovery to the coordinating center (MEE) to allow for proper reporting.

All observed or volunteered adverse events (serious or non-serious) and abnormal test findings, regardless of study group or suspected causal relationship to the study drug will be recorded in the subjects' case histories (source data, case report form). For all adverse events, sufficient information will be pursued and/or obtained so as to permit 1) an adequate determination of the outcome of the event (i.e., whether the event should be classified as a serious adverse event) and; 2) an assessment of the causal relationship between the adverse event and the study drug.

Adverse events thought to be associated with the study drug will be followed until the event (or its sequel) or the abnormal test finding resolves or stabilizes at a level acceptable to the Sponsor-Investigator and the study Medical Monitor.

Study staff will alert the treating physician immediately of any participant complaints or problems that are expressed to them. The site investigator and/or site study staff will report any unexpected and serious adverse events to the coordinating center (MEE) within 48 hours of discovery regardless of the assumed relation to the study intervention. The site investigator and the study staff will follow the reporting guidelines below.

➤ **Causality and Severity Assessment**

The Sponsor-Investigator of the IND application and the Medical Monitor (DSMC chair) will promptly review documented adverse events to determine 1) if there is a reasonable possibility that the adverse event was caused by the study drug(s); and 2) if the adverse event meets the criteria for a serious adverse event.

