## N = 68 subjects

**Preliminary Results:** Sixty-eight Kpros were implanted in 68 eyes (56 with previous sterile corneal ulceration) in 68 patients (15 with autoimmune disease) between 2017 - 2020 across 13 sites. The average age at the time of surgery was 62 [24-89] years, 42 (62%) subjects were male and 44 (65%) were white. The mean follow-up time was 91 weeks (SD= 47.6). A total of 20 KPros were removed with an average survival time of 70 [6-160] weeks.

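### Participation ends when the KPro or study tissue is removed, with only a limited 30-day tail, although all subjects are promised at least two years of follow-up; new harms after removal go uncaptured

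*Protocol*

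**What the plan says.** Three Protocol sections end participation at device or tissue removal:

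- **6.8 Rescue Medication or Therapy:** "Subjects who do not retain the cross-linked KPro will be withdrawn from the study". No later follow-up is mentioned.
- **8.8 Early Termination:** when an adverse event in the study eye is judged severe, the donor tissue is removed and replaced, "discontinuing the patient from further participation in the study". No later follow-up is mentioned.
- **10.3 Termination of Subjects due to Adverse Events:** "Termination from the study will happen if any of the following occurs", and KPro removal is on the list. The next paragraph covers an adverse event that forces the study tissue to be removed and replaced. In that case "prior to termination the patient will be followed for 30 days after replacement surgery".

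Three others point to longer collection, and none excepts device loss:

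- **8.9 Schedule of Activities, footnote:** "All subjects will be followed for at least 2 years".
- **8.6 Follow-up Procedures:** data from standard-of-care visits after week 52 are collected "in order to monitor subject safety for an additional 3 years or until study closure".
- **10.1 Recording Requirements:** "Adverse events thought to be associated with the study drug will be followed until the event" resolves or stabilizes.

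Neither the Protocol nor the SAP says how time after removal is treated in the safety analyses.

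**The concern.** Device loss or replacement is the primary endpoint (Protocol 11.1). Under 6.8, 8.8 and 10.3 it also ends observation for most other purposes. Safety is Objective 1 (Protocol 2.1). Adverse events of all subjects are to be summarised (11.6) and compared between arms (11.5 and the SAP's Secondary Analysis). Infectious keratitis and retinal detachment are events of special interest (9.1). The SAP's reorganised endpoint list treats time to vitritis and time to retroprosthetic membrane treatment as safety endpoints.

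If collection stops at removal, each of these is observed only for as long as the device survives, plus any tail. If cross-linking prolongs retention, the two arms are then watched for different lengths of time, and the missing time falls mainly on the control arm.

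**Working it through.** **The texts side by side**

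| Situation | What 6.8, 8.8 and 10.3 give | What 8.6 and 8.9 give |
|---|---|---|
| Adverse event forces removal; tissue replaced, with or without a new KPro | Termination, 30 days after replacement surgery (10.3) | At least 2 years; safety data for 3 more years after week 52 or until closure |
| Removal for another reason | Withdrawal or termination; no stated tail | Same |
| Removal without tissue replacement | Withdrawal or termination; no stated tail | Same |

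A site cannot satisfy both columns in any row. Section 6.8 adds a second difficulty: it names only the cross-linked KPro, and a masked site cannot tell which subjects have one.

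**How many subjects it reaches**

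1. Observed (SAP, opening summary): "A total of 20 KPros were removed" among 68 eyes. 20/68 = 29.4%. The average survival of those devices was 70 weeks (range 6 to 160).
2. Shortfall per removed eye against two years, taking 70 weeks as a mean and 2 years as 104 weeks: 104 − 70 = 34 weeks. The tail covers 30/7 = 4.3 weeks, leaving 29.7. Over 20 eyes, 29.7 × 20 is about 594 eye-weeks. This assumes that every removed eye gets the tail and could otherwise have been followed for 104 weeks. Given those assumptions it is a lower bound, because removals after week 104 contribute zero rather than negative time.
3. Planned losses by month 12 (Protocol 11.3: 84 subjects, 42 per arm, middle row of the table): control 42 × (1 − 0.55) = 18.9; active 42 × (1 − 0.85) = 6.3. Across all three rows the ranges are 17 to 21 control and 4 to 8 active.

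**How unequal the observation could be**

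Assume a constant hazard λ = −ln(12-month retention). Mean device time over 2 years is (1 − e^(−2λ))/λ, and the share of two-year person-time unobserved is 1 minus that over 2. For a 30-day tail after every loss, add (1 − e^(−2λ)) × 30/365.25 to the observed time.

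- Control, 0.55: λ = 0.598; observed 0.6975/0.598 = 1.167 years; unobserved 41.7%, or 38.8% with the tail.
- Active, 0.85: λ = 0.163; observed 0.2775/0.1625 = 1.708 years; unobserved 14.6%, or 13.5% with the tail.
- All three rows: 37–46% control and 10–19% active without a tail; 35–43% and 9–18% with it.

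The 30-day tail barely changes the imbalance. These are planning figures. The planned total by month 12 is 18.9 + 6.3 = 25.2 of 84 (30%), whereas the SAP's 29% accrued over all follow-up at an average of 70 weeks, so losses came later than planned and the real truncation is probably smaller.

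**The case against.** Much of the case on the other side stands.

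- A reader might infer three conflicting termination rules. Sections 6.8 and 8.8 are silent on a tail and do not forbid one, so they can be read together with 10.3. The firm contradiction is between termination at removal and the follow-up in 8.6 and 8.9; within 10.3, the bare KPro-removal item also sits awkwardly beside the 30-day paragraph.
- A reader might infer that an eye given no new device gets no further follow-up. Section 10.3 speaks of replacing the tissue with or without a keratoprosthesis, so a graft alone counts as replacement surgery. The gap is confined to removal for another reason or without donor tissue, and the documents do not show that either occurred.
- A reader might infer that late harms are never collected. Section 10.1 follows drug-associated events to resolution or stabilization, and counts events of unknown and questionable relationship as drug-associated for reporting.
- The primary endpoint is not harmed, because removal is the event.
- After removal the eye carries non-study tissue, and 9.1 defines safety through related events, so stopping collection is arguable. That bears on attribution and does not settle the conflict with 8.6 and 8.9; 11.6 also takes any adverse event from all subjects.
- The two-year horizon is itself loosely stated: 3.1 equates 2 years with week 52, the visit table ends at week 52, and mean follow-up was 91 weeks.
- No removals by arm are reported, so an imbalance between arms is a projection.

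**Conclusion.** The concern holds in a limited form. Participation ends at device or tissue removal, the only stated tail is 30 days after replacement surgery in adverse-event-driven cases, and this contradicts the follow-up promised to all subjects. What goes uncaptured is new-onset events after the tail and ongoing events judged unrelated. The adverse event comparison and the vitritis and retroprosthetic membrane endpoints are therefore truncated by the primary event.

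It affects 29% of implanted eyes on the SAP's count. Truncation would differ by arm if the treatment works: about 19 control against 6 active subjects leaving by month 12 under the middle planning row, which rests on the planned retention rates and 42 per arm. The documents do not support saying that the arms actually differed, that all post-removal safety data are lost, or that the retention result is biased. The point should be corrected, but it does not undermine the primary analysis.

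**What to change.** Reconcile Protocol 6.8, 8.6, 8.8, 8.9, 10.1 and 10.3 into one data-collection rule worded identically for both arms, replacing the reference in 6.8 to the cross-linked KPro alone. Under that rule, unless consent is withdrawn and subject to IRB approval, adverse events, acuity and further eye surgery continue to be abstracted from standard-of-care records after device loss, on the same horizon as for other subjects and whether or not tissue or a device is replaced. State that horizon consistently in 3.1, 8.6 and 8.9. This concerns data collection only; clinical management stays as the documents leave it, at the physician's discretion.

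The SAP should state how post-removal time is handled, and report events before and after removal separately as well as by randomised arm, because later events occur with non-study tissue in the eye.

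The cost is a protocol amendment and some coordinator time; 8.6 already has these items abstracted from six-monthly care visits. Subjects already terminated may need to be re-consented, and post-removal events will be harder to attribute.

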11. STATISTICAL METHODS/DATA ANALYSIS

11.1 Primary endpoint(s) or outcome measure(s)

- Time from surgery to device loss or replacement

11.2 Secondary endpoints or outcome measure(s)

- Twelve-month retention rate
- Incidence of delayed epithelial healing at day 30 (week 4 visit)
- Cornea thickness metrics measured by AS-OCT; at week(s) 1, 4, 16, 24, and 52.
- Time from surgery to retroprosthetic membrane treatment (laser or surgical interventions)
- Time from surgery to occurrence of vitritis (sterile or infectious)
- Time from surgery to occurrence of ocular surgery to address melt, including partial graft.

11.3 Sample Size Determination

To determine the number of subjects to enroll, we performed sample size calculations based on a review of keratoprosthesis retention rates from prior studies and conservative estimates of efficacy in the treatment arm. For the control arm, we used twelve-month retention rates ranging from 50 to 60%, which has been reported in autoimmune eyes at high risk for keratoprosthesis loss. Therefore, we anticipate the twelve month retention rate for the untreated (not cross-linked) cornea will be 50-60%. To estimate the retention rate in the treatment arm, we reviewed the retention rates from the two published case reports that describe cross-linking of the keratoprosthesis carrier cornea in high-risk eyes (Kanellopoulos et. al. & Robert). While the two case reports describe a 100% retention rate in a total of 12 eyes at one year, the exact retention rate for a multicenter study is not known. Using a two-sided log rank test for equality of survival curves, we performed sample size calculations so that we could detect a 30% difference in retention rate between the treatment group and the control group and specified the probability of type 1 error of 0.05, a study power of 80%, a follow up period of twelve-months, and a 4% loss to follow up. In order to detect a difference between the control arm and the treatment arm using

these considerations, the calculations resulted in sample size estimates between 82 and 88 subjects (Table 2). For practical purposes, we also took into consideration the time available for the study and the number of high risk keratoprosthesis procedures performed at each study site. Using the mid-range estimates, we aim to enroll 84 subjects into this study.

Eighty-four subjects will be randomized equally to treatment or control group. Randomization will be stratified by 16 centers, as well as two pre-operative diagnostic categories: autoimmune disease vs. prior corneal melt without autoimmune disease. Eye with a history of autoimmune disease may have a different risk of a new melt than eye that have a history of a prior corneal melt. Thus there will be a total of 32 strata. Stratification will ensure balance of the stratification factors between the two arms of the study. A number of blocks of varying size will be determined (e.g. 5 blocks of size 4, 6 blocks of size 2) and randomization assignments will be prepared accordingly. Since we have 32 strata, relatively small block sizes will be planned to minimize the chance of large departures from the desired allocation ratio that could occur due to incomplete blocks by the time of completion of patient recruitment. Although the ability of the clinical staff to predict future treatment assignments is increased due to smaller block sizes, we do not think that this will be a major issue for the present study.

Retention Rate for Control Group	Retention Rate for Treatment Group	Total Sample Size
0.50	0.80	88
0.55	0.85	84
0.60	0.90	82

11.4 Analysis Population

N/A

11.5 Effectiveness Analysis

We will conduct an initial analysis to examine if distributions of baseline characteristics are balanced between the two treatment groups in our randomized study. Standard descriptive statistics will be reported, median (min-max) for numerical variables and frequency count (%) for categorical variables. Comparisons of numerical characteristics between treatment groups

will be conducted using the Mann-Whitney Wilcoxon test. Comparisons of categorical characteristics will be conducted using Chi-square, or Fisher's exact test as appropriate.

Primary Analysis

The primary efficacy analysis will follow an intent-to-treat analysis strategy including all randomized eyes. The major goal of this study is to determine the efficacy of using a collagen cross-linked cornea as a carrier for the Boston Keratoprosthesis in preventing corneal melts and increasing the retention of the keratoprosthesis. The primary endpoint of the efficacy analysis is time from surgery to device loss or replacement. Kaplan-Meier plot of event free survival by treatment groups will be provided and log-rank test will be used to examine if survival curves are significant different between groups. In addition, we will use a proportional hazards regression model to test the effectiveness of using a collagen cross-linked cornea as a carrier for the Boston Keratoprosthesis in preventing corneal melts and increasing the retention of the keratoprosthesis. We will obtain an estimate (95% CI) of the hazard ratio of device loss comparing treatment with control. This framework allows for the control of covariates, which may be unbalanced by chance despite the randomization of treatment assignment. If Kaplan-Meier plots of event free survival by study time, or related plots of log (-log) (survival) indicate violations of the proportional hazards assumption, then weighted log-rank test will be used according to strategies described by Peckova and Fleming.

Secondary Analysis

We plan to conduct a number of pre-specified analyses of secondary study endpoints. Analyses of secondary “time-to-event” type endpoints (time to retroprosthetic membrane treatment and time to occurrence of vitritis) will use the Kaplan-Meier approach with log-rank test and Cox proportional hazards regression, similar to the primary analysis for time to device loss. Comparison of cornea thickness metrics at week 1, 4, 16, 24, and 52 for treatment versus control group will be performed using the Mann-Whitney Wilcoxon test at each time point. Furthermore, mixed model will be used to examine the effect of time, treatment and interaction between them on cornea thickness. Comparison of twelve-month retention rate and incidence of delayed epithelial healing at Day 30 (week 4 visit) between groups will be performed using Chi-square

test, or Fisher's exact test as appropriate. In addition, the occurrence of any adverse events will be described and compared between treatment arms of the study.

